6.2.5 Pre-specified Subgroups Analysis

Subgroup analysis of the primary outcomes are planned to assess effect modifiers, specifically:

- ξ Age (under 2 months, 2 – 12 months, 13 – 59 months) – as recorded at Day0
- ξ Sex (male, female) – as recorded at Day0
- ξ Presentation with cough or difficulty breathing (yes, no) – as recorded at Day0
- ξ Diagnosis (severe, non-severe)
- ξ Referral (yes, no)
- ξ Antimicrobial drug prescription (yes, no). Antimicrobials are defined as antimalarials and antibiotics, according to the same definition used for the outcomes.
- ξ Stratification factors (location and facility type)

Effect modification will be assessed by incorporating an interaction between the time period and the potential effect modifier in the model, acknowledging that power will be low. Stratified model results will only be presented if the interaction term is significant, defined as p-value<0.2.

For interim analyses and DMC analyses, no subgroup analysis is planned.

² Urgency, as reported by the caregiver, was only collected in Tanzania. For India, urgent referrals will be defined based on the registry alone, as described for the primary analysis.

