3.3 The TIMCI project

The Tools for Integrated Management of Childhood Illness (TIMCI) project builds on this hypothesis to form part of the response to the need for better mechanisms to detect and manage children with severe illness in LMICs. It is a 4 year UNITAID-funded project, focused on the interventions of pulse oximetry and CDSAs in primary care, organised into four main outputs: (1) introduction of pulse oximetry and CDSAs in four countries (India, Kenya, Senegal and Tanzania); (2) evidence generation for pulse oximetry and CDSA introduction; (3) market strengthening for adapted multi-modal devices; and (4) creating conditions for national and global scale-up and sustainable use of these tools.

This protocol focuses on the evidence generation component of the TIMCI project in India and Tanzania (a separate protocol has been developed for Kenya and Senegal to reflect a different study design).

To our knowledge, no large scale studies have systematically evaluated the health impact, cost-effectiveness and optimal implementation approaches of pulse oximetry, alone or embedded into a CDSA, for children with a broad range of clinical diagnoses in primary care.

4 Goal & objectives

The overall goal of the TIMCI project is to reduce morbidity and mortality in sick children attending primary care facilities, while supporting the rational and efficient use of diagnostics and medicines by healthcare providers. The evaluation component of the project seeks to generate evidence on the health impact, operational priorities, cost and cost-effectiveness of introducing pulse oximetry, alone or embedded into a CDSA, into primary care in LMICs, for children 0 – 59 months of age, to facilitate national and international decision-making on scale-up. Specific objectives, according to these themes, include:

Health and quality of care impact

To evaluate the impact on health and quality of care outcomes of sick children 0 – 59 months of age of introducing pulse oximetry, alone or embedded into a CDSA, for facility-based primary care, compared to routine care, including on:

- Mortality and hospitalisations
- Adherence by primary healthcare providers to key components of assessment, classification and management guidelines, in particular on referral decision-making and antimicrobial prescription

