To assess severe, moderate and mild hypoxaemia prevalence among sick children attending intervention primary care facilities, and understand the association of different hypoxaemia cut-offs with adverse outcomes, according to sociodemographic and clinical features.

Implementation and process

- To understand the facilitators and barriers to uptake, acceptability of the intervention and behaviour change by health care providers, caregivers and their children, and a variety of stakeholders at community, health facility, national and international levels
- To evaluate characteristics of children, caregivers, healthcare providers and health facilities associated with uptake and impact of the interventions
- To understand how the interventions affect patient flow and patient-provider interactions, including change in care processes, consultation time, and communication between caregivers and healthcare providers

Cost and cost-effectiveness

- To determine the cost and estimate any cost savings and/or additional costs of introducing pulse oximetry with or without CDAs into primary care in four countries
- To estimate cost effectiveness of the interventions compared to routine care and other interventions aimed at improving the management of severe illness in children 0 – 59 months of age

5 Study design

Health and quality of care impact are evaluated through pragmatic, parallel group, cluster randomised controlled superiority trials in India and Tanzania, and quasi-experimental pre-post studies in Kenya and Senegal.

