5.1 Pilot phase

The pilot phase will occur over an estimated 3-month period prior to the start of the definitive pragmatic cluster RCT. It will serve to ensure the intervention package is optimised (Part I) before roll-out to all study facilities, allow for stabilisation of the intervention (Part II) and for piloting of the research instruments and processes. It will also allow certain mixed methods sub-studies to be conducted in the intervention arms prior to intervention start, to allow for comparison within the same facilities over time.

The RCT dataset collected during this pilot phase will be used for exploratory analysis of early implementation, but will not be included in the definitive RCT analysis. Mixed methods study data collected during this phase will be incorporated into the overall analysis to facilitate the understanding of the implementation processes, mechanisms and context in order to inform the development of the package for scale.

Part I – refining the intervention and piloting research processes

We will select 2 – 4 facilities per trial arm to tailor the introduction of the intervention, based on qualitative feedback from healthcare providers and caregivers (in-depth interviews, informal discussions) and key stakeholders (key informant interviews), combined with observation of the way in which pulse oximetry and CDSAs are used (from SPA observation and exit interviews, process mapping and time-flow, and training assessments conducted by PATH). These studies, further detailed in study-specific sections below, will aid understanding of implementation processes with a focus on acceptability, and barriers and facilitators to implementation to inform potential refinement of the approach to training, supervision, caregiver engagement and guidance on where to use the devices within the care process.

In addition, we will conduct a pre-intervention (baseline) assessment in a sample of study facilities in each arm, in which we will collect the RCT dataset, SPA assessments and facility-based process mapping and time-flow study to allow for comparison within the same facilities over time.

Concurrently, we will pilot the research instruments and processes and refine if necessary, including eligibility screening, participant information and consent, and data collection tools.

We estimate this phase will take 4 – 6 weeks, but will extend if more major adjustments are necessary (to intervention package, or to the protocol).

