6.4.2 Pragmatic cluster RCT

Two primary outcomes will be assessed in order to improve the ability to detect a difference between intervention and control arms, given the relatively low occurrence of severe outcomes at primary care level:

- Proportion of children with a severe complication (death or secondary hospitalisation) by Day 7
 - Secondary hospitalisation refers to any delayed hospitalisation (occurring at any point greater than 24 hours after Day 0 consultation) and any hospitalisation occurring without referral. The denominator is all enrolled children

- Proportion of children admitted to hospital within 24 hours of the Day 0 primary care consultation and as a result of a referral
 - This is used as a proxy for 'appropriate referral' of children, as those with severe disease should generally be admitted to hospital. The denominator for this outcome is also all children enrolled in the study, rather than only referred children. This is because the proportion of referred children that are admitted may be high in routine care, in the context of an inappropriately low referral rate. The aim of the intervention is therefore to increase the overall referral rate of children with severe disease. Hospital admission is chosen as the proxy of severe disease rather than using primary care classification of severe disease, as there are inadequacies in the classification of severe disease in routine practice

The trial will be interpreted as positive if either primary outcome is positive with no indication of harm from non-significant outcomes. This will be assessed separately in India and Tanzania and will also be assessed across the two countries for the sub-group of children presenting with cough or difficulty breathing.

We anticipate that we will see a greater effect on the 'appropriate referral' outcome, given that increasing detection and referral of children with severe disease is the focus of the intervention, and that morbidity and mortality among children with severe disease is highly contingent on quality of care at hospital level, which is not the focus of the intervention. Whilst hospital admission is still contingent on factors beyond the remit of the intervention (e.g. on caregiver completion of referral and hospital bed availability), it is not dependent on quality of care during hospital admission.

Secondary outcomes:

- Proportion of children with severe complication (death or secondary hospitalisation) by Day 28

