If we fail to reject the null hypothesis H_{12} then we will stop and this point and conclude that the study is negative as neither of the co-primary outcomes were significant. If we reject the null hypothesis H_{12} then we would go on to test H_1 and H_2 . If $p_2 \leq \alpha_2$ then we reject H_2 and test H_1 as $p_1 \leq \alpha$. If $p_2 > \alpha_2$ then we do not reject H_2 and test H_1 as $p_1 \leq \alpha_1$.

All outcomes will be evaluated regardless of the outcome of the first evaluation. For each intervention arm, the overall trial will be interpreted as positive if either primary outcome is

positive compared to control. This will be assessed separately in India and Tanzania and will also be assessed across the two countries.

Missing data on key endpoints is to be expected due to the pragmatic nature of the study. If substantial data are missing (e.g. >10%), a set of sensitivity analyses shall be carried out where missing data are handled following different approaches such as, best/worst case scenario, complete cases, simple imputation or multiple imputation with chained equations (71, 72). The impact of each method on the primary outcomes results will be taken into account when interpreting the final analysis results. Further information on missing data handling will be detailed in the SAP.

We will conduct planned subgroup analysis of the primary outcomes to assess effect modifiers, specifically age, sex, clinical presentation (particularly cough / difficulty breathing) and diagnosis (particularly severity classification) and healthcare provider decision-making (particularly referral and antimicrobial prescription). Effect modification will be assessed by incorporating an interaction between trial arm and the variable in the model, acknowledging that power will be low. Planned sensitivity analysis will be conducted including only the first disease episode of each child during the study period (as some children may attend the facility on more than one occasion over the 12-month period). Further exploratory analysis will be detailed in the SAP.

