1 ADMINISTRATIVE INFORMATION

1.1 Document Scope

This document provides a detailed description of the methodologies that will be followed, as closely as possible, when analysing and reporting results from TIMCI RCT study. The planned analysis detailed in this document is in compliance with that briefly specified in the TIMCI RCT protocol, except if otherwise detailed.

The purpose of this Statistical Analysis Plan is to:

- ξ Ensure that the analysis is appropriate for the aims of the study, reflects good statistical practice in general, and minimises bias.
- ξ Ensure that the analyses performed are consistent with the conditions of the protocol.
- ξ Explain in detail how the data will be handled, covariates derived and analysed to ensure transparency and reproducibility, including enabling others to perform the actual analysis in the event of sickness or other absence.
- ξ Protect the project by helping it keep to timelines and within scope.

Additional exploratory or auxiliary analyses of data not specified in the protocol or this document are permitted but fall outside the scope of this Statistical Analysis Plan. Where analyses are presented which are not included in the SAP, these will be clearly indicated as such along with a justification as to their inclusion.

The analysis strategy will be made available if required by journals or referees when the main papers are submitted for publication. Additional analyses suggested by reviewers or editors will, if considered appropriate, be performed in accordance with the analysis plan, but if reported, the source of such post-hoc analyses shall be declared.

This document is written following the guidelines outlined in Gamble et al. [1]

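### SAP 6.2.5 tests effect modification against a time period that this trial does not have, and lists referral and antimicrobial prescription, which the intervention is meant to change, as modifiers

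*SAP*

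**What the plan says.** SAP 6.2.5 plans subgroup analyses of the two primary outcomes. The method is: "Effect modification will be assessed by incorporating an interaction between the time period and the potential effect modifier in the model". Stratified results are shown only if the interaction p-value is below 0.2. The listed modifiers are age, sex, cough or difficulty breathing, diagnosis (severe or not), referral, antimicrobial prescription and the stratification factors.

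Protocol 8.3.1 gives the method as: "Effect modification will be assessed by incorporating an interaction between trial arm and the variable in the model". Its modifiers include "diagnosis (particularly severity classification) and healthcare provider decision-making (particularly referral and antimicrobial prescription"). SAP 1.1 describes the planned analysis as "in compliance with that briefly specified in the TIMCI RCT protocol, except if otherwise detailed". SAP 6.2.5 does not announce a departure.

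Three other places bear on the modifiers:
- Protocol section 4 names as an objective the effect on "Adherence by primary healthcare providers to key components of assessment, classification and management guidelines, in particular on referral decision-making and antimicrobial prescription".
- SAP 3.1.4 lists Day 0 referral as a secondary outcome, and antibiotic and antimalarial prescribing as other outcomes.
- SAP 6.1.2.1 and 6.1.2.3 use referral to define both primary outcomes.

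**The concern.** There are two separate problems.

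First, the interaction term is the wrong one. An interaction between calendar or study period and a child's characteristic says nothing about whether the intervention works differently in different children. SAP 1.1 says the document should let someone else run the analysis, and that person would find no period variable to use.

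Second, a subgroup contrast keeps the protection of randomisation only if the subgrouping variable cannot be affected by the intervention. All children are enrolled after facilities are allocated, so timing relative to allocation is not the test. Age and sex cannot be changed by the consultation. Referral and prescribing are decisions made in it. If the arms refer or treat different kinds of children, the referred (or treated) children in one arm are not comparable with those in the other.

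At stake is the reading of which children benefit, not the trial's main result.

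**Working it through.** **1. The interaction term.** The design offers no time period that could be meant.
- SAP 3.1.1 describes a parallel-group cluster trial, and SAP 6.2 defines no period term.
- Pilot data "will not be included in the definitive RCT analysis" (Protocol 5.1).
- The before-after comparisons belong to the "quasi-experimental pre-post studies in Kenya and Senegal" (Protocol section 5), which have their own protocol.

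Protocol 8.3.1 names trial arm, and the SAP commits to the protocol unless it says otherwise. The SAP wording is therefore an error in a stated analysis rule.

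**2. Referral inside the primary outcomes.**
- Appropriate hospitalisation (SAP 6.1.2.3) counts an admission only if the child had referral advice. At the planned rates of 1.5% and 1.95% (1.5% × 1.3), Tanzania's 22 × 1,680 = 36,960 children per arm give 36,960 × 0.015 = 554 and 36,960 × 0.0195 = 721 events. All are in referred children; unreferred children have 0 v 0. No arm effect exists in that stratum, so the interaction cannot be estimated. The convergence remedy in SAP 6.2.1 (dropping or combining clusters) cannot fill a cell that is empty by definition.
- Severe complication (SAP 6.1.2.1): apart from deaths, an admission within 24 hours counts only if the child was not referred. The same admission is thus an event or not depending on the subgroup variable.

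**3. How large could a spurious effect on severe complication be?** The documents give no referral rate, so this is an illustration.

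Inputs from the documents: control risk 1.1%; appropriate hospitalisation rising from 1.5% to 1.95%; 36,960 per arm.

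Assumptions:
- 75% of referred children are admitted within 24 hours in both arms.
- Already and newly referred children have a 10% risk of death or later admission, whether or not referred.
- Newly referred children would not otherwise have been admitted within 24 hours.
- There is no true effect: overall risk is 1.1% in both arms.

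Calculation:
- Referred share: 1.5%/0.75 = 2.0% in control; 1.95%/0.75 = 2.6% in intervention.
- Unreferred risk, control: (1.1% − 2.0% × 0.10)/98.0% = 0.90/98.0 = 0.918%.
- Unreferred risk, intervention: (0.90% − 0.6% × 0.10)/97.4% = 0.84/97.4 = 0.862%.
- Ratio 0.862/0.918 = 0.94. The referred stratum is 10% v 10%.

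Chance of display, ignoring clustering, with variance of each log odds ratio = Σ[1/(np) + 1/(n(1−p))] over the two arms:
- Referred: about 74 and 96 events; log OR 0; SE 0.163.
- Unreferred: about 333 and 310 events; log OR −0.063; SE 0.079.
- Interaction: z = 0.063/√(0.163² + 0.079²) = 0.063/0.181 = 0.35, p = 0.73.
- Probability that |Z| exceeds 1.282 (p<0.2): about 23%, against 20% with no interaction.

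Varying the admitted share over 50–100% and the risk over 5–15%, the unreferred ratio runs from 0.80 to 0.98. The chance of display is 20–31%, except at the extreme corner (50% admitted, 15% risk), where it is about 60%.

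**The case against.** The strongest reply has four parts.

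*The time-period wording is a slip that the protocol already corrects.* An analyst would probably see it and use trial arm. That lowers the risk, but the SAP is the operative document and this is the sentence that defines the test. It should be right.

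*The subgroup results could not mislead much.* This largely stands. A reader might infer that splitting by referral would hide a real gain in appropriate hospitalisation. The documents do not support that. Protocol 6.4.2 and SAP 6.1.2.3 use all enrolled children as the denominator, and that result is reported whatever the subgroups show. For this outcome the referral interaction yields no valid p-value, so the display rule gives no ground for showing strata. The defect is an analysis that cannot run. A reader might also infer that a false benefit on severe complication would probably be shown; the calculation above does not support that over most of its range.

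*Referred children are already analysed as a denominator elsewhere.* True: SAP 6.1.2.3 adds that proportion. Protocol 6.4.2 explains why it is not the main measure ("the proportion of referred children that are admitted may be high in routine care, in the context of an inappropriately low referral rate"), but does not forbid reporting it. It can stay as a description; it should not be presented as a subgroup effect of the intervention.

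*Diagnosis severity and the differing lists.* SAP 6.2.5 gives no source for severity, so it cannot be called post-consultation with certainty. Protocol 6.4.2 names only age, sex and cough or difficulty breathing, and SAP 3.1.4 puts some of the same factors among exploratory analyses outside its scope. A reader might call this a contradiction. It is weak evidence of one, since factors associated with outcomes are not the same as modifiers of the arm effect.

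**Conclusion.** The point holds as a correction to the subgroup plan. The interaction term in SAP 6.2.5 is wrong for this design and conflicts with Protocol 8.3.1. Referral and antimicrobial prescription should not be tested as effect modifiers, because the intervention aims to change them and they are reported as outcomes. The arm-by-referral interaction for appropriate hospitalisation cannot be estimated. These conclusions rest on the text and need no assumption.

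The practical size is modest. The primary comparison, alpha and sample size are untouched. Any numerical distortion depends on assumed referral and risk figures, and in the central illustration it would be displayed barely more often than chance. For prescribing, the protocol's only figures come from studies of other decision-support tools and cover antibiotics alone, whereas the SAP modifier also includes antimalarials. They do not establish the direction or size of bias in this trial, least of all in the arms with pulse oximetry only.

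**What to change.** In SAP 6.2.5:
- Replace the time period with trial arm: each intervention arm against control in Tanzania, pulse oximetry against control in India.
- Remove referral and antimicrobial prescription as effect modifiers, and report them by arm as the outcomes they already are.
- Keep diagnosis severity as a modifier only if it is defined from pre-consultation information; otherwise report it descriptively.
- Define cough or difficulty breathing from the caregiver's pre-consultation report. SAP 4.2 gives both that definition and one based on the provider's diagnosis, and 6.2.5 does not choose.
- Retain age, sex and the stratification factors.

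Amend Protocol 8.3.1 to match, or record the departure and its reason in the SAP.

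The cost is wording, with no new data. Up to three listed subgroup analyses are lost (referral, prescription and possibly severity). A protocol amendment may need submission to ethics committees and registries under Protocol 10.2; recording the departure in the SAP is the alternative. Appropriate hospitalisation among referred children would still be reported under SAP 6.1.2.3.

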- Proportion of children cured (defined as caregiver reported recovery from illness) at Day 7 follow-up
- Proportion of children referred by a primary care healthcare provider to a higher level of care (either to a hospital or to an inpatient part of a larger primary healthcare facility) at Day 0 consultation

Proportion of children who completed referral, as reported at day 7 follow-up
Other outcomes of interest – hypoxaemia (in intervention arms only)

- Proportion of children with severe ($\text{SpO}_2 < 90\%$), moderate ($\text{SpO}_2 90 - 91\%$) and mild hypoxaemia ($\text{SpO}_2 92 - 93\%$), adjusted for sites at high altitude
- Proportion of children with hypoxaemia (according to differing cut-offs) with severe complication
- Proportion of children with severe hypoxaemia not meeting any other clinical criteria for severe disease

- Proportion of children referred with hypoxaemia who receive oxygen at hospital

Other outcomes of interest – referral and follow-up

- Proportion of children with non-severe disease referred to a higher level of care on Day 0
- Average length of stay (in days) of children admitted to hospital
- Proportion of children attending scheduled follow-up at the same facility by Day 7
- Proportion of children presenting for unscheduled follow-up to any health facility by Day 7

Other outcomes of interest – antimicrobial prescription

- Proportion of children prescribed an antibiotic at Day 0
- Proportion of children prescribed a diagnosis-appropriate antibiotic
- Proportion of febrile children tested for malaria at Day 0
- Proportion of malaria positive children prescribed an antimalarial
- Proportion of malaria negative children prescribed an antimalarial
- Proportion of untested children prescribed an antimalarial

Sub-groups for analysis of primary and secondary outcomes:

- Age (under 2 months, 2 – 12 months, 13 – 59 months)
- Sex
- Presentation with cough / difficulty breathing

Other factors for exploratory analyses

- Additional sociodemographic characteristics urban / rural location, distance from health facility, key household indicators such as maternal age and education
- Main complaint / symptom categories (including cough / difficulty breathing, fever, diarrhoea and other) and time since onset of symptoms
- Alternative hypoxaemia cut-offs
- Healthcare provider severity classification
- Facility and health system factors – type of facility, healthcare provider qualification and previous training

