6 ANALYSIS

Analyses will follow Consolidated Standards of Reporting Trials (CONSORT) guidelines [10] and will be performed and reported overall and by country.

Outcomes will be presented separately for young infants (<60 days) and older children (60 days-59 months), the malaria-related outcomes will be presented only on older children.

Results of interim analyses and DMC analyses will be presented overall in the open report and by intervention arm in the closed report.

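### Showing subgroup estimates only when the interaction p-value is below 0.2 lets the data decide which pre-specified results are reported, and can withhold the cough/difficulty-breathing estimate that the protocol plans without condition

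*SAP*

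**What the plan says.** SAP 6.2.5 plans subgroup analyses of the two primary outcomes by age, sex, cough or difficulty breathing, diagnosis, referral, antimicrobial prescription, and the stratification factors (location and facility type). The cough entry reads "Presentation with cough or difficulty breathing (yes, no) – as recorded at Day0". The test is an "interaction between the time period and the potential effect modifier in the model, acknowledging that power will be low". The display rule follows: "Stratified model results will only be presented if the interaction term is significant, defined as p-value<0.2".

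The protocol differs in three ways.

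- Section 8.3.1 has no display filter and names a different interaction: "Effect modification will be assessed by incorporating an interaction between trial arm and the variable in the model, acknowledging that power will be low".
- Section 6.4.2 lists age, sex and cough/difficulty breathing, without condition, under "Sub-groups for analysis of primary and secondary outcomes".
- Section 6.4.2 also says that the rule for calling the trial positive "will also be assessed across the two countries for the sub-group of children presenting with cough or difficulty breathing".

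Elsewhere the SAP plans a pooled cross-country analysis (3.7) and gives the testing procedure (4.1). Neither section mentions cough.

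**The concern.** The rule selects pre-specified results on their own p-value. Estimates that pass do so because the subgroups look different. Estimates that agree, which are the evidence for a consistent effect, are left out. The SAP concedes low power, so p≥0.2 is weak evidence of uniformity and a poor reason to withhold an estimate.

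The cough/difficulty-breathing subgroup matters most. The protocol attaches an assessment of the primary-outcome verdict to it, and in Tanzania cough is one of the criteria for using the oximeter. If its estimate appears only when the interaction passes, readers may never see it.

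**Working it through.** **1. Planning figures (used only to supply numbers and risks).** Protocol 6.6.1: control risk of severe complication 1.1%, 30% reduction to 0.77%, 80% power, alpha 0.05 (taken as two-sided), ICC 0.001. The two-proportion formula with pooled variance gives 13,351 per arm before clustering.

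- Tanzania: design effect 1 + (1680 − 1) × 0.001 = 2.679. Then 13,351 × 2.679 ≈ 35,768, or 21.3 clusters, rounded up to 22 (36,960 per arm).
- India, initial three-arm plan: design effect 1.509. This gives about 20,147, or 39.5 clusters, rounded up to 40 (20,400 per arm).

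Both stated sizes reproduce.

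**2. How often the filter passes by chance.** SAP 6.2.5 names 8 factors; with 2 primary outcomes that makes 16 tests per comparison. One cannot be estimated. SAP 6.1.2.3 counts appropriate hospitalisation only in children referred at Day 0, so unreferred children have no events by definition. At most 15 remain.

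- Expected to pass with no true interaction: 15 × 0.2 = 3.0.
- Chance of at least one: 1 − 0.8^15 = 0.965, if independent.

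The expected count does not need independence; the 96% does.

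**3. Exaggeration of the contrasts shown.** For a one-degree-of-freedom test, p<0.2 means |z| > 1.2816. If the interaction statistic is normal with mean μ and variance 1, its mean when shown is μ + [φ(1.2816 − μ) − φ(1.2816 + μ)] / P(shown).

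| True μ | P(shown) | Mean z when shown | Ratio to truth |
|---|---|---|---|
| 0.5 | 0.255 | 1.34 | 2.7 |
| 1.0 | 0.401 | 1.88 | 1.9 |
| 1.5 | 0.589 | 2.15 | 1.4 |
| 2.8 | 0.936 | 2.94 | 1.05 |

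**4. Cough split, Tanzania, same effect in both groups.** Assumptions: common OR 0.70, control risk 1.1% in both groups, and 55% with cough (Protocol 6.3 gives 40–70%).

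- Control events: 36,960 × 0.55 × 0.011 = 224 with cough, and 36,960 × 0.45 × 0.011 = 183 without.
- Standard error of the difference in log ORs, ignoring clustering: 0.156. With the full design effect: 0.156 × √2.679 = 0.255.
- With no true interaction the median |z| is 0.674 over all trials and 1.645 among those shown.
- Median ratio of the two subgroup ORs, no clustering: exp(0.674 × 0.156) = 1.11 for all, exp(1.645 × 0.156) = 1.29 for shown.
- With the full design effect: 1.19 for all, 1.52 for shown.

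Cough varies within facilities, so the full design effect is an upper bound and no design effect a lower one.

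**5. How often the cough estimate is withheld (severe complication, Tanzania, one arm versus control).**

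| True effect | No design effect | Full design effect |
|---|---|---|
| Same in both groups | 80% | 80% |
| Only in cough (RR 0.70 v 1.00) | 13–16% | 42–46% |
| Stronger in cough (RR 0.70 v 0.85) | 49–53% | 67–69% |

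Ranges cover cough shares of 40–70%. Worked case at 55%, effect only in cough: the log-OR difference is 0.360 and the standard error with the full design effect is 0.243, so μ = 1.48 and 42% are withheld. In India with 60 clusters per arm, the effect-only-in-cough figures are 18–22% and 30–34%.

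**The case against.** The strongest defence is that gating on interaction guards against spurious subgroup claims, that subgroups lie outside the alpha procedure of SAP 4.1, and that this is a matter of reporting. It is true that no primary test changes. But a 0.2 gate is a poor guard: with 15 tests at least one chance finding is very likely to pass, and the gate displays the most divergent contrasts.

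Several stronger readings are tempting, and the documents do not support them.

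- A reader might see a conflict with SAP 6, where "Outcomes will be presented separately for young infants (<60 days) and older children (60 days-59 months". There is none. That is a two-group split at 60 days shown without condition; the filter covers stratified model results for a three-level age factor. Both can be followed.
- A reader might infer that concordant results vanish altogether. The rule withholds stratified model results; the SAP does not say whether non-significant interaction estimates or p-values are also left out.
- A reader might infer that the cross-country verdict rests on cough alone. Protocol 8.3 and 8.3.1 and SAP 3.7 plan a pooled analysis with no such restriction.
- A reader might infer that the filter cancels the Protocol 6.4.2 assessment. SAP 1.1 says the SAP complies with the protocol unless otherwise detailed, so that assessment may stand apart. But the SAP never specifies it. SAP 6.4 shows primary outcomes by indication group, but SAP 4.2 combines cough with young age and IMCI classification in Tanzania, so this is no substitute.

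The 80% figure is simply 1 − 0.2 and holds in any trial with equal effects. The other withheld percentages are for single-country comparisons; a pooled analysis has more events and would withhold a real difference less often.

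**Conclusion.** The point holds as a reporting defect. The filter makes the reporting of pre-specified subgroup estimates depend on the data, without support in the protocol and against the SAP's own admission of low power. With no effect modification, 3.0 of at most 15 estimates per comparison pass by chance. The exaggeration is an average effect on the between-subgroup contrast: large when the true interaction is weak, almost nil when it is strong.

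The cough/difficulty-breathing estimate can be withheld; the documents do not show that it must be. The sizes rest on equal control risk in both groups, the assumed effects, the 40–70% cough share, and a design effect between 1 and 2.679. The 96% also needs independence, which is doubtful because the outcomes and several factors are related.

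All of this assumes that the interaction is with trial arm. As written, the SAP names time period; read literally, the gate would not test effect modification by arm at all.

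**What to change.** In SAP 6.2.5:

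1. Delete the p<0.2 condition.
2. For the baseline subgroups (age, sex, cough/difficulty breathing, location, facility type), always present events/n, OR, risk difference, 95% CI and interaction p-value, for example in a forest plot.
3. Replace time period with trial arm in the interaction, as in Protocol 8.3.1.
4. State that the pooled cough/difficulty-breathing analysis of Protocol 6.4.2 is always reported.
5. Diagnosis, referral and antimicrobial prescription arise after allocation and may be changed by the intervention. Show them, if at all, as descriptive only, and omit referral for appropriate hospitalisation.

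The cost is a revised SAP paragraph and one more table or figure. No new data are needed and the primary tests do not change.
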